1. Referrals from VA health providers, including primary care providers, geriatricians, endocrinologists, and other subspecialist who care for diabetic patients.
2. Direct advertisement through local newspaper and at the VA for potential subjects.
3. Referrals from the VA Ann Arbor MOVE! program. The MOVE! program in VA Ann Arbor provided care for 710 veterans in 2010, with 490 of them as first time participants in MOVE! program;⁶¹ 50% of the MOVE! participants have diabetes.⁶²
4. We will obtain VA Institutional Review Board's approval to screen for diabetic patients using the VA electronic medical record. After identifying potential subjects, we will contact their primary providers for approval to recruit these patients.

Sample:

[figure not shown]
We will recruit approximately 70 veterans who have known diabetes and are aged ≥ 60 years. Subjects will be recruited based on their self-reported diabetes diagnosis. After identifying potential subjects, we will send them introductory letters describing the study, including an opt-out postcard for them to mail back. If we do not receive the opt-out postcard after 2 weeks, then we will contact the veterans by phone to confirm their interest in participating in the study and to screen for eligibility.

Eligibility

Inclusion Criteria

- Aged ≥ 60 years
- Diagnosis of diabetes mellitus, type 2 (or adult-onset) (self-reported or per medical record)
- At least 5/6 on 6-item cognitive screening test on the phone
- Ability to reliably operate the Actiwatch accelerometer
- Community-living (i.e., not nursing home resident)
- Ambulatory either with or without an assistive device
- English-speaking
- Competent to provide informed consent
- Sedentary (< 150 min moderate activity in a week)

Figure 3.

Exclusion Criteria

- Medically unstable in which exercise would be contraindicated (e.g., previous severe symptomatic hypoglycemia, decompensated congestive heart failure, severe anemia, severe aortic stenosis, unmanaged thyroid dysfunction, etc.)
- Self-reported illness or conditions that impair cooperation with the study team or ability to complete study procedures
- Hospitalization within last 6 months for any reason
- 2 or more days of complete bed rest within the last month
- Limb hemiplegia or amputation
- Replacement of any hip or knee joint within the last 6 months
- Current attendance in a PA program
- Work involves shift schedule
- Heart attack within past month
- Parkinson's disease

PARTICIPANT TIMELINE

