Figure 3 describes the study flow. After potential subjects are identified based on inclusion and exclusion criteria, they will be asked to complete a number of questionnaires to obtain baseline information on PA, social participation and contextual environment. They will then be taught to wear a wrist-worn accelerometer for 7 days to monitor home activities. Subjects who successfully completed the baseline 7-day home monitoring will be randomized into 2 arms: intervention or wait- list control groups. The intervention group will receive the tailored PA report in a one-hour counseling session, followed by weekly phone calls for 4 weeks by the same occupational therapist. This will be followed by monthly phone calls by research assistants until the end of the study.

The wait-list control group will receive monthly phone calls to discuss about their health status but not PA-related issues. These monthly phone calls are necessary to maintain the subjects' interest in staying in the trial. The wait-list control will receive the tailored PA pattern report and the counseling intervention at the end of the study.

Both arms of the study will have post-intervention assessment at 5 weeks after randomization and final outcomes assessment 6 months after randomization. Each outcomes assessment involves surveys, physical function assessment, and a 7-day home monitoring period. After the 6-month assessment, we will interview participants who completed the intervention to assess their experience for the purpose of improving the intervention in the future.

Research Procedures

Baseline data collection: Aim 1

If potential participants meet the inclusion and exclusion criteria based on phone screening, then they will be invited for baseline evaluation. Baseline data collection will be completed in 4 steps from 3 sources: accelerometer-generated PA patterns, the ecological momentary assessment (EMA) of contextual environment, and survey data. We estimate the time to complete baseline assessment will be 1.5 - 2 hours.

1. After participants complete the screening and informed consent, a trained research assistant will assess their physical performance, which includes the Six-Minute Walk Test ⁶⁴ and Timed Up and Go Test ⁶⁵.

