5. After the face-to-face session, the same OT will make weekly phone calls to the participants for 4 weeks (See Appendix for a Flowchart of the Phone Call). The OT will already have been trained by [name] group to make these phone calls following the flowchart, demonstrated an understanding of the program, learned to address the various actions on the flowchart (i.e., how to probe for barriers, how to help with problem solving, etc.), and how to respond to participants' various questions. The OT will ask the participant questions based on their response to the PA worksheet as described above. Then, using the answers to the PA worksheet as a guide, the OT will review with participants the steps of the self-regulation, provide positive reinforcement, assess progress in achieving PA goals, problem solve barriers, and discuss changes in medications and health status. Each phone call will last approximately 30 minutes. This completes the intervention phase of the study.

Wait-list control group

This group will participate in all outcome assessments as the intervention group at baseline, post-intervention, and 3-months and final assessments. After the 6-month final assessment, these participants will receive their baseline activity summary reports and the counseling that the intervention group had received.

Post-intervention assessment

Post-intervention assessment will be done 5 weeks after randomization to assess if the intense intervention (counseling and weekly phone calls) had an immediate impact on the study participants. Potential participant drop outs are expected at the 6-month follow-up. Therefore, information obtained at the post-intervention assessment will be helpful in determining the impact of the intervention. All participants in the intervention group and wait-list control group will be assessed for all outcomes, including the 7-day home monitoring.

After the post-intervention assessment, a RA will contact all participants monthly until the 6-month final assessment to discuss changes in medications and health status. PA issues will not be discussed. The goals of these phone calls are to obtain updated health information and maintain the participants' interest in remaining in the trial.

Measures

Primary outcomes:

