Strategies for Ensuring Treatment Fidelity Treatment fidelity is defined as “the procedures used to monitor and enhance the reliability and validity of behavioral interventions,” and is an essential component of our study. Per recommendations from the National Institutes of Health (NIH) behavior change consortium,⁷¹ we will use several strategies to ensure treatment fidelity in this study. The strategies that we will use include standardized modules for the intervention and delivery of the intervention, interventionist (i.e., occupational therapist) training and monitoring based on previously developed protocol by [name] group. Another area of treatment fidelity that we will address relates to how the treatment is received by the participant. This involves an assessment of individual factors such as comprehension of information, and the ability to use and perform skills associated with both the data collection and behavioral elements of the study. We have a standardized interactive learning module to teach the participant how to input ecological momentary activities in the wrist-worn accelerometer. Because the validity of the ecological momentary activity information is central to our tailoring methods, all participants will undergo this learning module prior to their first session with the OT. At the end of the study, we will conduct interviews with each participant to examine their experiences in the intervention including adherence with steps of the self-regulation process.

Statistical Analysis

Univariate analyses

Before conducting formal analysis for each specific aim, descriptive analyses will be performed based on univariate statistics, using t-tests for continuous variables or chi-square tests for categorical variables. This will involve inspection of univariate statistics such as mean, median, standard deviation, skewness and kurtosis for continuous variables, and frequency tabulations for categorical data. We will also inspect for outliers and inspect bivariate plots of PA and participation data over time for each person to identify outliers in the bivariate relationships. All analyses, including descriptive statistics and model fitting, will be carried out using SAS for Windows, release 9.2 (SAS Institute, Inc., 2002-2008, Cary, NC, USA).

Primary analyses

Aim 1: To examine the relationship between PA, contextual environment (physical and social environment), and social participation, among veterans with diabetes.

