Hypothesis 2a: *At the end of 6 months, individuals in the intervention group will have increased PA compared to the control group.* PA is measured in 3 ways using Actiwatch and CHAMPS (Table 5), so three separate analyses will be done using each measure – Actiwatch daily average counts and weekly counts, and CHAMPS weekly measurement.

The primary analysis is based on comparing the 6-month change in PA between treatment group and control group by t-tests. To adjust for potential confounding, separate models of multivariate regression analyses will be conducted with each measure of PA as the dependent variable, randomization arm as a predictor, baseline PA as a covariate, and potential confounders including age, sex, diabetes status, and number and perception of environment barriers will be included in the model. Assuming that residuals from the model fit are normally distributed, the analysis is equivalent to a classical analysis of covariance. For data that does not fit a normal distribution, inverse, logarithmic or power transformations will be performed or generalized linear models (GLM) with Poisson or gamma error will be considered.

To further assess if the pattern of PA changed, i.e., whether the change in PA occurred across each day or just a few days in a week, we will graphically compare the daily average counts at 6-month follow-up for the intervention group with the control group (Figure 5). For example: If Y_{ij} = daily average counts at day_j over 7 days after intervention for subject i and j = 1 (d1), 2 (d2), ..., 7(d7), then we will try to fit the linear mixed model to test if the slopes of the two PA curves are the same and test for overall difference ($\beta_1 = 0$):

$$Y_{ij} = \beta_0 + \beta_1 * \text{intervention} + \beta_2 * \text{days} + \beta_3 * z + \epsilon_{ij}$$

With this small sample of 28-35 participants per treatment group, it is possible that the study may be underpowered to determine significant differences between groups. However, the results will provide essential information about the actual effect size of the treatment which will allow us to better estimate the sample size needed for a larger trial.

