where BA=outcome at baseline; G=intervention group; CF= one or more contributing factors; TIME= time variable; *=interaction between variables. The key aspects of this model for hypotheses 2a and 2b are interactions G*TIME and CF*TIME, and the magnitude and significance of these interaction effects provide insight into mechanisms underlying study group differences. The remaining terms are used to reflect study design and adjust for baseline values. This analysis will yield three tests: 1) a test for outcome changes over time of the study, 2) a test of the intervention vs. control group differences (an intervention effect), and 3) a test for interaction of intervention effect with time. As in the primary hypothesis, we are primarily interested in the overall intervention effect. However, a changing intervention effect over time, as reflected in intervention by time interaction is of great interest since it might suggest that the intervention has a greater impact as time progresses, which would provide support for long-term effect of the intervention. The following methods will be considered: linear mixed effects (LME) models for continuous variables with normally distributed residuals; and generalized linear models (GLM). Both of these methods allow for unbalanced data, time-varying covariates, and structured covariance matrices. Repeated measures models will be developed in the framework of linear mixed effects (LME) models or generalized linear mixed effects models (GLMM).

AIM 3: To assess participant satisfaction with the intervention, we will use a series of Likert scale satisfaction items and a semi-structured interview protocol including open-ended questions to obtain feedbacks. A quantitative analysis and a qualitative analysis will be performed for this aim:

- Results from the Likert scale satisfaction items will be analyzed to identify the association between different characteristics of the study participants and their satisfaction with the intervention. Participant characteristics (e.g., age, sex, race, education background, functional status, co-morbidities, etc.) will be cross-tabulated with the satisfaction outcomes, which can be dichotomized into satisfied or not satisfied. Individual relationships will be assessed using χ^2 tests. Multiple logistic analyses will be used to analyze responses according to each factor, controlling for socio-demographic variables.

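### Aim 3's adjusted logistic models and chi-square tests of satisfaction are likely to be unstable with about 28–35 raters

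*Combined protocol and SAP*

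**What the plan says.** The quantitative part of Aim 3 (Statistical Analysis, Aim 3) uses Likert satisfaction items. Participant characteristics are to be "cross-tabulated with the satisfaction outcomes, which can be dichotomized into satisfied or not satisfied". Six characteristics are named as examples (age, sex, race, education, functional status, co-morbidities) in an open-ended list. Each is tested by chi-square, and then: "Multiple logistic analyses will be used to analyze responses according to each factor, controlling for socio-demographic variables". No cut-point, expected satisfaction rate, limit on adjusters or sparse-data method is given.

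On who answers:

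- The Participant Timeline, describing what follows the last outcome visit, says: "we will interview participants who completed the intervention to assess their experience for the purpose of improving the intervention in the future".
- Table 3 places intervention feedback at 6 months.
- The Wait-list control group section says: "After the 6-month final assessment, these participants will receive their baseline activity summary reports and the counseling that the intervention group had received". At 6 months that arm has had nothing to rate.
- Strategies for Ensuring Treatment Fidelity is broader: at the end of the study "we will conduct interviews with each participant to examine their experiences in the intervention".

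On numbers, the Sample section says "We will recruit approximately 70 veterans who have known diabetes and are aged ≥ 60 years". Hypothesis 2a adds: "With this small sample of 28-35 participants per treatment group, it is possible that the study may be underpowered". That caution concerns differences between groups and is not carried over to Aim 3.

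**The concern.** A logistic model's information depends on the smaller outcome group. If most people are satisfied, few are left in the other group, and several adjusters soon exhaust them. Two problems follow. Under separation, a covariate or combination of covariates sorts the outcomes perfectly, so no finite maximum-likelihood estimate exists. Where the fit does converge, large odds ratios can appear by chance. Chi-square tests on the same sparse tables rest on small expected counts.

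Aim 3 exists to refine the intervention before a larger trial. An odds ratio of 4 or 5 that is only noise could be read as showing whom the programme suits.

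**Working it through.** **Inputs from the documents.** N is about 70 in two arms intended to be equal, and 28–35 per arm is the plan's own figure. The model is one factor plus socio-demographic variables. Taking these as age, sex, race and education gives 5 terms.

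**The plan's figure.** 70 / 2 = 35 gives the upper end. 28 = 35 × 0.80 would follow from a 20% loss, but no dropout rate is stated, so the lower end is consistent with N = 70 without being derivable from it.

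**Assumptions, not in the documents.** Satisfaction is 50–90%. Covariates are either evenly split (balanced) or include 10% women and 20% of minority race (unbalanced). Every true odds ratio is 1.

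**Step 1: events per term.** Smaller outcome group = n × (1 − p); divide by 5 terms.

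| Satisfied | Not satisfied, n = 28 | n = 35 | Per term, n = 28 | n = 35 |
|---|---|---|---|---|
| 50% | 14 | 17.5 | 2.8 | 3.5 |
| 80% | 5.6 | 7 | 1.1 | 1.4 |
| 90% | 2.8 | 3.5 | 0.6 | 0.7 |

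**Step 2: why a rare covariate level matters.** With 10% women, the expected number is 28 × 0.10 = 2.8 to 35 × 0.10 = 3.5. Take three. The chance that all three fall in the same outcome group is p³ + (1 − p)³: 0.125 + 0.125 = 0.25 at 50% satisfied, 0.512 + 0.008 = 0.52 at 80%, and 0.729 + 0.001 = 0.73 at 90%. Any of these events makes the sex coefficient infinite.

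**Step 3: simulated fits with no true association.**

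- *Balanced, five or six terms, n = 28–35.* Failure (separation or non-convergence) occurs in about 0–7% of fits at 50–70% satisfied, 11–28% at 80% and 52–72% at 90%. With five terms the range over all settings is about 0–68%.
- *Unbalanced, five terms.* Separation, from 300 runs per setting:

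| Satisfied | n = 28 | n = 35 |
|---|---|---|
| 50% | 46% | 32% |
| 70% | 55% | 44% |
| 80% | 75% | 61% |
| 90% | 85% | 86% |

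At 90% satisfied, a further 6% (n = 28) or 3% (n = 35) of runs had everyone in one outcome group, so no model could be fitted. Repeated simulation puts the unbalanced range at about 31–91%.

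- *Fits that did converge.* With balanced covariates the median of the largest spurious odds ratio is about 3–6, and it is higher in the sparsest unbalanced case. In the unbalanced five-term runs, 35–66% of converged fits had at least one odds ratio above 5 or below 0.2.
- *Smaller models, unbalanced.* With three terms, separation is still 13–68% at n = 28 and 4–54% at n = 35.

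**Step 4: chi-square.** Expected count = n × (share not satisfied) × (share at that factor level). At 20% not satisfied and the most favourable 50/50 factor: 28 × 0.2 × 0.5 = 2.8 and 35 × 0.2 × 0.5 = 3.5. Both are below 5, and they shrink further as fewer are dissatisfied or the factor is less even. For a level held by 10% of people, the whole margin is only 2.8–3.5, so its expected counts are below 5 at any satisfaction rate.

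**The case against.** Several points on the other side are fair.

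- **Failure is conditional.** A reader might infer that the models will often fail to converge. The documents do not support that as a general statement, because they give no satisfaction rate, cut-point or covariate mix. With evenly split covariates and 50–70% satisfied, failure is 0–7%. With 20% minority race but sex split evenly, it is about 5% at 50% satisfied and n = 35. Large spurious odds ratios remain in these settings, so instability stands where outright failure does not.
- **Six or more factors in one model is not what the text says.** It reads as one factor at a time with socio-demographic adjustment, and functional status and co-morbidities are not socio-demographic. The five-term figures above use this reading and lead to the same conclusion.
- **Dichotomizing is optional.** True, but it is the only outcome coding described, and the logistic step presupposes it or something close to it.
- **The rater set is not fixed.** If all 70 were rated, six balanced terms would fail in about 0.2% of fits at 80% satisfied and 13% at 90%. With unbalanced covariates, five-term separation would be 5–61% over 50–90% satisfied. Feedback at 6 months and later counselling of the wait-list arm favour the smaller set, but the passages need reconciling.
- **The consequence is limited.** A reader might also infer that these odds ratios would send the revision of the intervention in the wrong direction. Semi-structured interviews are planned, and their themes are also meant to guide improvement. Infinite estimates are usually visible to an analyst. Aim 3 is exploratory.

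**Conclusion.** The point holds as a minor one. With about 28–35 raters and about five terms per model, adjusted odds ratios for satisfaction are likely to be unstable. Over an assumed 50–90% satisfied, fits separate or fail in about 0–68% of cases with balanced covariates and about 31–91% with 10% women and 20% minority race. The median largest spurious odds ratio is about 3–6 in the balanced case. Chi-square expected counts are below 5 once 20% or fewer are not satisfied. The direction is robust; the size depends on the satisfaction rate, the covariate mix and the rater set, none of which the documents fix. The Aim 2 efficacy comparisons are not affected.

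**What to change.** In the Aim 3 analysis text:

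1. State the analysis set and time point, reconciling the Participant Timeline with the treatment fidelity section.
2. Keep the Likert scale, and report each item's distribution with confidence intervals.
3. Examine each factor singly on the ordinal score, by Spearman correlation, Wilcoxon test or a one-factor proportional-odds model.
4. Use Fisher's exact test where a table is sparse.
5. If an adjusted binary model is kept, fix the cut-point in advance, use Firth penalization with at most one adjuster, and label it exploratory. Fewer adjusters alone do not suffice, as the three-term results show. Even with two terms, 80% satisfied gives only 5.6 / 2 = 2.8 to 7 / 2 = 3.5 events per term.

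The cost is wording only, since all the data are already to be collected. The loss is fully adjusted odds ratios, which a sample of this size is unlikely to support.

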Hypothesis 2b: At the end of 6 months, individuals in the intervention group will have improved social participation (ability to participate and satisfaction with participation). Social participation will be measured with the PROMIS questionnaires with a population mean of 50 and standard deviation of 10. The change in *social participation* will be compared between the treatment and control groups by t-tests, similar to the analysis plan described for *Hypothesis 2a*. Multivariate regression analyses will be conducted to evaluate confounding factors, with social participation as the dependent variable, randomization arm as a predictor, baseline social participation as a covariate. Potential confounders including age, sex, co-morbidities, and number and perception of environment barriers will be included in the model. Distribution of the residuals from model fit will be examined, and additional transformations and generalized linear models will be considered.

Additional analyses:

Further exploration of effects at each time points are of interest. Models will utilize outcome measurements at all time-points (baseline, 5 weeks, and 6 months). Different outcome measures and covariates can be evaluated. Repeated measure longitudinal models can be considered:

For example: **Outcome at 5 weeks and 6 months = BA + G + CF + G*TIME + CF*TIME,**

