- Qualitative analysis plan will be directed by mentors and consultants, and the PI will be taking formal courses to learn qualitative analyses. The goal of this analysis is to identify if there are uniform themes in the feedbacks provided by the study participants to inform improvement of future intervention.

Secondary analyses

For change in functional status, biomarkers, and quality of life at 6-month follow-up, separate linear regression analyses will be performed, adjusting for important covariates (age, sex, co-morbidities, etc.). Effect of the intervention on the outcomes will be analyzed using a simple follow-up analysis: $y_{i1} = B_0 + B_1 X_i + \epsilon_i$, where y_{i1} is the follow up measurement at 6-month follow up, B_1 is the change in mean outcomes at follow up between the 2 treatment groups, and X_i is the membership of being in the intervention group.

Data Management: Data will be entered using case report forms created in Microsoft Access with encrypted password-protected file and stored on a pass-word protected desktop computer in a locked office. Each record

will include 1) variables to uniquely identify the subject, 2) the source of the data, 3) site, 4) date, and 5) data collector. We will train the RA to enter data into the database. To protect against potential breach of identifiable information of the research subjects, a master list containing their identifiable information and the study identifier will reside on the VA computer server, accessible only by the PI and RA.

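### The secondary treatment effect is taken from a model of the 6-month value on arm alone; it does not match the sentence before it, and the outcome's own baseline value is not named

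*Combined protocol and SAP*

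**What the plan says.** The Secondary analyses section has two consecutive sentences on these outcomes.

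- The first reads "For change in functional status, biomarkers, and quality of life at 6-month follow-up, separate linear regression analyses will be performed", with adjustment for age, sex, co-morbidities and an open-ended remainder.
- The second reads "Effect of the intervention on the outcomes will be analyzed using a simple follow-up analysis" and displays y_i1 = B_0 + B_1 X_i + e_i. Here y_i1 is the 6-month measurement, X_i is arm, and B_1 "is the change in mean outcomes at follow up between the 2 treatment groups".

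All three outcome groups are measured at baseline. Table 3 marks each of them there, the Baseline data collection section has the walk and Up and Go tests at that visit, and the Biomarkers item has A1c and body mass index at baseline and 6 months.

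For the primary outcomes, Hypothesis 2a says "The primary analysis is based on comparing the 6-month change in PA between treatment group and control group by t-tests" and then adds regressions "with each measure of PA as the dependent variable, randomization arm as a predictor, baseline PA as a covariate". Hypothesis 2b likewise adds regressions "with social participation as the dependent variable, randomization arm as a predictor, baseline social participation as a covariate".

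**The concern.** As worded, the two sentences do not describe one model. The first speaks of change and lists covariates. The second has a 6-month value as its outcome and no covariates. It is unclear whether the listed covariates enter the model that yields the effect. It is also unclear whether change means change from baseline or, as in the definition of B_1, only the difference between arms. Two analysts could follow the section and report different estimates and intervals.

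On every reading, the outcome's baseline value is not named as a covariate. That value is often the strongest single predictor of the 6-month value. Leaving it out loses precision when the two are moderately or highly correlated. Using a change score instead loses most when the correlation is low. In a trial that describes its groups as "With this small sample of 28-35 participants per treatment group", interval width matters for what the pilot can say about these outcomes.

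**Working it through.** **Inputs.** The group size n is 28 to 35 per arm (Hypothesis 2a). The plan gives no standard deviation or baseline to 6-month correlation r for any of these outcomes, so r = 0.3, 0.5, 0.7 and 0.9 are assumptions. Equal arms, equal SDs at both visits and complete 6-month data are also assumed. The plan states no precision figure for this analysis, so there is none to reproduce.

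**Large-sample variance of the arm effect**, in units of (2/n)·SD²:

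- 6-month value on arm only: 1
- change from baseline on arm: 2(1 − r)
- 6-month value on arm and baseline: 1 − r²

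Relative to the baseline-adjusted model, arm-only is 1/(1 − r²) and the change score is 2(1 − r)/(1 − r²) = 2/(1 + r).

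**Finite-sample cost.** Adding k covariate terms multiplies the expected variance by 1 + k/(2n − k − 3).

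- Baseline alone (k = 1): 1 + 1/52 = 1.019 at n = 28; 1 + 1/66 = 1.015 at n = 35.
- Baseline plus three terms, for example age, sex and a co-morbidity score (k = 4): 1 + 4/49 = 1.082; 1 + 4/63 = 1.063.

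**95% interval half-width in SD units.** Arm-only is t(2n−2)·√(2/n), which is 0.54 at n = 28 and 0.48 at n = 35. Adjusted is t(2n−2−k)·√[(2/n)(1 − r²)·cost]. For r = 0.7, n = 28, k = 1 this is 2.006 × √(0.0714 × 0.51 × 1.0192) = 0.39.

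| | r = 0.3 | 0.5 | 0.7 | 0.9 |
|---|---|---|---|---|
| Arm-only / adjusted variance, large sample | 1.10 | 1.33 | 1.96 | 5.3 |
| Change / adjusted variance, large sample | 1.54 | 1.33 | 1.18 | 1.05 |
| Arm-only / adjusted after cost, k = 1, n = 28 | 1.08 | 1.31 | 1.92 | 5.2 |
| Arm-only / adjusted after cost, k = 4, n = 28 | 1.02 | 1.23 | 1.81 | 4.9 |
| Arm-only / adjusted after cost, k = 4, n = 35 | 1.03 | 1.25 | 1.84 | 4.9 |
| Adjusted half-width, k = 1, n = 28 | 0.52 | 0.47 | 0.39 | 0.24 |
| Adjusted half-width, k = 4, n = 28 | 0.53 | 0.48 | 0.40 | 0.24 |
| Adjusted half-width, k = 1, n = 35 | 0.46 | 0.42 | 0.34 | 0.21 |
| Adjusted half-width, k = 4, n = 35 | 0.47 | 0.43 | 0.35 | 0.21 |

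The k = 4 rows assume that the three extra covariates explain nothing.

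**Where adjustment stops helping.** Against arm-only, break-even is r = √(1 − 1/cost): 0.14 (n = 28) and 0.12 (n = 35) for baseline alone, and 0.27 and 0.24 with three uninformative covariates as well. Against the change score with baseline as the only covariate, the crossover is r = 2/cost − 1, or 0.96 and 0.97. Beyond that the change score is better by less than 2% in variance.

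**Simulation check.** With 28 per arm, no true effect and 20,000 trials per r, the arm-only to adjusted variance ratios were 1.08, 1.31, 1.93 and 5.27 for k = 1, and 1.01, 1.23, 1.83 and 4.96 for k = 4. All mean estimates were within 0.005 SD of zero, so no bias appeared.

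**The case against.** **The two sentences may be two analyses.** The primary hypotheses pair an unadjusted t-test with an adjusted regression, and this section could be meant the same way. That is a fair reading. But the text does not say so or say which analysis counts, and the baseline value is unnamed in both.

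**The plan is not silent on baseline.** If change means change from baseline, the baseline value enters through the outcome, and the open-ended covariate list could cover it. The Additional analyses section also plans models that use all time points, with an example that includes the outcome at baseline. However, that section is exploratory and permissive: "Different outcome measures and covariates can be evaluated. Repeated measure longitudinal models can be considered". Its example model uses 5-week values, which Table 3 does not schedule for biomarkers. The Missing Data section adds baseline variables only if they turn out to be associated with loss to follow-up. None of this binds the secondary analysis.

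**The gain could be smaller than shown.** If age, sex and co-morbidities do enter the effect model, they may already absorb part of what the baseline value would explain. Suppose they explain 20% of the variance at both visits through the same component. The partial correlation is then (r − 0.2)/0.8, and the large-sample variance ratio of leaving baseline out against putting it in is about 1.02, 1.16, 1.64 and 4.3 at the four values of r. This point stands: the benefit is negligible at r = 0.3 and remains material at 0.7 and above.

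**Severity.** The arm-only analysis is valid, and the size of the loss rests wholly on assumed correlations. That is accepted and limits the weight of the point.

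**Conclusion.** The concern holds. The plan takes the secondary intervention effect from an arm-only model, does not reconcile it with the preceding sentence, and does not name a baseline value that it collects and already uses in the adjusted primary regressions. This is a matter of efficiency and prespecification. With complete 6-month data there is no bias over randomizations.

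The loss ranges from almost nothing at r = 0.3 to roughly a doubling of variance at r = 0.7 and about fivefold at 0.9, under equal SDs and correlations that the documents do not supply. The importance is modest, because these are secondary outcomes in a pilot that says it may be underpowered. The plan should still be changed, because the remedy is simple and uses data already being collected.

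**What to change.** For each functional status, biomarker and quality-of-life outcome, state one model for the intervention effect:

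y_i1 = B_0 + B_1 X_i + B_2 y_i0 + e_i,

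with y_i0 the baseline value of that outcome. Decide now whether age, sex and co-morbidities stay. If they do, write them into the equation and replace the open-ended ending with the full list. Describe B_1 as the baseline-adjusted difference between arms at 6 months, and reword the opening sentence to match. If an unadjusted comparison is also wanted, label it supportive.

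No new data are needed. In expected variance, the baseline term alone costs 1.9% at 28 per arm and 1.5% at 35. With three further covariate terms the total cost is 8.2% and 6.3%. The break-even correlations in the working show when each is recovered.
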